Although there is no perfect method for estimating a causal effect in observational data (10), conceptual frameworks exist to guide the design and analysis of observational studies in order to limit apparent paradoxes and common biases and increase the transportability of estimates (3,11). In fact, causal inference from observational databases can be viewed as an attempt to emulate a randomised experiment (the "Target Trial") to answer the question of interest (3). In this study, the effectiveness of SARS-CoV-2 primary vaccination in preventing SARS-CoV-2 infection is assessed across national borders, using a framework for causal inference. The well-defined causal analysis methodology will subsequently be deployed across federations to reproduce the analysis and pool the aggregated results. We aim to inform high-level vaccine policy by leveraging real-world observational data from multiple data sources hosted in multiple sites (i.e., countries).

Research guestion/objectives

We aim to investigate the real-world effectiveness of SARS-CoV-2 primary vaccination as compared to partial or no vaccination in preventing SARS-CoV-2 infection in virtually all resident populations spanning different countries. The study will be conducted in two sequential stages, expanding the exercise to several countries/regions:

- Stage I (pilot): Aragon (Spain) and Belgium.
- Stage II: Aragon (Spain), Belgium, Austria, Finland, Norway, Estonia and The Netherlands. The participation of these countries/regions is conditional on data access.

Methodology

Study design and context

The study design is an observational retrospective longitudinal (cohort) study using routinely collected administrative, social, health and care data from several

countries/regions in Europe. We have designed the observational study to emulate a hypothetical Target Trial (TT) of the causal effect of SARS-CoV-2 vaccination programmes in preventing SARS-CoV-2 infections.

Target Trial specification and emulation

The key components of the target trial and its subsequent emulation are explicitly described in Table 1. Several of the key components are part of the widespread population, intervention, control, and outcome (PICO) approach to the formulation of clinical questions (12).

Protocol Component	Target Trial Specification (Ideal Hypothetical Trial)	Target Trial Emulation (Actual Study Design reusing Real World Data)

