In the sequential emulated target trial (Figure 2), each eligible individual is considered as a different individual at each eligible time (i.e., *daily*). As such, a sequence of nested (*daily*) trials are emulated with increasing time $(t_1, t_2, ..., t_n)$, iterating over the days in the enrollment period. At each eligible time during the enrollment period, the vaccination status of eligible individuals is assessed and every individual who has completed a primary vaccination schedule at that time (treated/exposed) is matched to an individual who has not (yet) completed the primary vaccination schedule (control). Newly vaccinated individuals (completing a primary vaccination schedule) are eligible for inclusion in the study, even if they had previously been selected in the "no (or partial) vaccine group". Follow-up ends at diagnosis of SARS-CoV-2 infection, death, death of matched person, completed primary vaccination (for unvaccinated or partially vaccinated controls), completed primary vaccination of the matched control (for primary vaccinated persons), booster dose (for primary vaccinated persons), booster dose of the matched vaccinated person (for unvaccinated or partially vaccinated controls), or the end of the study period. The study period ends at the most recent date at which data is available at the time of analysis. The data extraction period starts from the date of the first documented SARS-CoV-2 infection, in order to appropriately identify individuals with a previously documented SARS-CoV-2 infection.

[figure not shown]

Figure 1. Timeline of the target trial (ideal hypothetical trial).

BY-COVID is funded by the European Union's Horizon Europe research the European Union and innovation programme under grant agreement number 101046203.

[figure not shown]

Figure 2. Timeline of the sequential emulated target trial (actual study design reusing Real World Data).

BY-COVID is funded by the European Union's Horizon Europe research the European Union and innovation programme under grant agreement number 101046203.

Sources of information

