Randomization is mimicked by matching on all confounding factors required to ensure comparability (conditional exchangeability) of the groups defined by vaccination (as identified in the Directed Acyclic Graph, see causal model specification published in Zenodo (13)). For each day during the enrollment period (i.e., sequential emulated trial), all newly vaccinated individuals (i.e. those having completed the primary vaccination schedule) will be matched in a 1:1 ratio to unvaccinated (or partially vaccinated) controls based on the variables listed in the adjustment set to close non-causal backdoor paths and so, eliminate confounding bias (16): age, gender, residence area, pregnancy, being an essential worker, being institutionalised, being a foreigner, presence of comorbidities, and the immune status. Presence of comorbidities is defined as having one of the following conditions: diabetes, obesity, health failure, COPD, a solid tumour without metastasis, chronic kidney disease, sickle cell disease, chronic liver disease, and hypertension (see the data model specification published in Zenodo (13) for variable-level specification, including data dictionaries and crosswalks defining each variable using several international disease *classification systems*). Immune status is defined as having one of the following conditions: HIV infection. blood cancer, transplantation, primary immunodeficiency, immunosuppression (see the data model specification published in Zenodo (13) for variable-level specification and crosswalks).

The matching will be performed using exact matching (whenever possible) or distance based algorithms such as nearest neighbour matching based on the Mahalanobis distance based on the probability of intervention (vaccination) for those individuals not matched using exact matching. Covariate balance after matching will be evaluated considering mean differences between variable values (standardised for continuous variables) between vaccinated and unvaccinated groups, with a difference of 0.1 or less considered to be acceptable.

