For each person, follow-up ends at the occurrence of the outcome event (i.e., a confirmed SARS-CoV-2 infection), death (all causes), completing primary vaccination (for unvaccinated or partially vaccinated controls), completing primary vaccination of the matched control (for vaccinated persons), vaccination with a booster dose (for vaccinated persons), vaccination with a booster dose of the matched vaccinated person (for unvaccinated or partially vaccinated controls), or the end of the study period (i.e., the most

BY-COVID is funded by the European Union's Horizon Europe research the European Union and innovation programme under grant agreement number 101046203.

recent date at which data is available at time of analysis). Newly vaccinated persons (completing a primary vaccination schedule) are eligible for inclusion in the study, even if they have previously been selected as a control. As such, the matched controls enrolled at a particular day during the enrollment period are those who are unvaccinated (or partially vaccinated) at this date but may receive a first (or second) vaccination dose at a later date during the data extraction period.

Differences in the occurrence of a SARS-CoV-2 infection (as a time-to-event outcome) between primary vaccinated and unvaccinated or partially vaccinated individuals (average treatment effect, ATE (16)) will be computed by using adjusted Cox proportional-hazards models (17), and hazard ratios (HRs) and a robust variance estimate will be obtained.

A secondary analysis will be performed where the effectiveness of primary vaccination in preventing SARS-CoV-2 infection is assessed for different vaccine brands (e.g. BioNTech-Pfizer, Moderna, Johnson-Johnson, Astrazeneca, Novavax), hence conducting a stratified analysis using the matched pairs constructed for the primary analysis. Further, we can assess vaccine effectiveness during different time periods, with a dominant circulation of different SARS-CoV-2 variants.

Several sensitivity analyses will be performed accounting for different imputation algorithms, and different matching algorithms and compared in covariate balance after matching, robustness of the survival estimate and computing efficiency of the algorithm.

HRs and variance estimates will be collected from each country or region, and a meta-analysis will be performed in which the HRs are pooled by using the inverse variance method (18).

Ethical aspects

Balance risk/benefit

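### The protocol labels its estimand the average treatment effect, but one-way matching and a Cox model give a hazard ratio in matched vaccinated people

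*Protocol*

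**What the plan says.** The Statistical analysis plan section sets the contrast as "Differences in the occurrence of a SARS-CoV-2 infection (as a time-to-event outcome") between primary vaccinated people and those unvaccinated or partially vaccinated. It labels this contrast the average treatment effect ("average treatment effect, ATE (16)) will be computed by using adjusted Cox proportional-hazards models") and states that "hazard ratios (HRs) and a robust variance estimate will be obtained". Country-level hazard ratios are then pooled by inverse variance.

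The matching runs in one direction. The same section says that on each day "all newly vaccinated individuals (i.e. those having completed the primary vaccination schedule) will be matched in a 1:1 ratio to unvaccinated" or partially vaccinated controls. The text on the sequential emulated trial, under Target Trial specification and emulation, agrees: each exposed person "is matched to an individual who has not (yet) completed the primary vaccination schedule (control"). On method, "The matching will be performed using exact matching (whenever possible) or distance based algorithms"; no caliper is given, and no rule for vaccinated people left without a match.

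Three other places bear on the target:

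- The objective concerns "preventing SARS-CoV-2 infection in virtually all resident populations spanning different countries".
- Table 1, Eligibility criteria (emulation column), leaves out people who have neither a registered dose nor a positive diagnosis.
- Table 1, Causal contrast of interest, gives the observational counterpart of the per-protocol effect and does not say over which population it is averaged.

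**The concern.** An average treatment effect averages over the covariate distribution of the whole eligible population. Controls picked to resemble the vaccinated carry the covariate distribution of the vaccinated, so the contrast applies to them. The label also pairs a difference in occurrence with a model whose only stated product is a ratio of hazards.

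At stake is what the study may conclude. The ATE label, read with the objective, invites the result to be taken as the effect in nearly all residents. What is estimated is the effect in vaccinated people who found a control, in a dataset without undosed and undiagnosed residents. Each country's hazard ratio averages over its own matched vaccinated mix, and those are the quantities pooled.

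**Working it through.** The protocol gives no figure for this point, so there is nothing to reproduce. The check has two parts.

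**1. Design against label**

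- An ATE needs matching in both directions, or weighting or standardisation to the eligible population. The protocol describes none of these.
- Matching starts from the vaccinated, so the target is the effect in the vaccinated if all are matched, or in the matched vaccinated if some are not.
- A difference in occurrence needs a risk or survival contrast at a stated time. None is named.
- Because undosed and undiagnosed residents are absent, even an ATE computed in this dataset would not be that of all residents.

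**2. Could the label matter numerically?**

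*Illustration A, full matching.* Assumed: people aged 65+ are 20% of the population, hazard ratio 0.2 below 65 and 0.5 at 65+, equal baseline risk. From the protocol's introduction: uptake 83% (Belgium) and 92% (Aragon) by the end of 2022. With share *s* aged 65+, the average is approximately 0.2(1 − s) + 0.5s = 0.2 + 0.3s.

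- Population, s = 0.20: 0.2 + 0.06 = 0.260.
- All people aged 65+ vaccinated: s = 0.20/0.83 = 0.241, giving 0.272; s = 0.20/0.92 = 0.217, giving 0.265. The gaps are 1.2 and 0.5 points of effectiveness.
- Opposite extreme, all unvaccinated people aged 65+: s = 0.03/0.83 = 0.036, giving 0.211; s = 0.12/0.92 = 0.130, giving 0.239. The gaps are 4.9 and 2.1 points in the other direction.

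*Illustration B, with and without matching loss.* All inputs assumed: two equal strata, constant hazards, 168-day control risks 5% and 10%, hazard ratios 0.2 and 0.5, uptake 70% and 95%. Stratum hazards over 168 days are −ln 0.95 = 0.0513 and −ln 0.90 = 0.1054. At the start of follow-up the hazard ratio is Σwλθ / Σwλ, where w is the stratum weight, λ the control hazard and θ the stratum hazard ratio.

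| Target | Weights | Ratio at start | Limit of a marginal Cox fit over 168 days |
|---|---|---|---|
| Whole population | 1 : 1 | 0.402 | 0.401 |
| All vaccinated | 0.70 : 0.95 | 0.421 | 0.420 |
| Matched vaccinated, each control used once and controls run out | 0.15 : 0.025 | 0.277 | 0.275 |

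- With the stratum hazard ratios reversed (0.5 and 0.2), the Cox limits are 0.300, 0.280 and 0.425.
- With equal uptake of 85% in both strata, all three targets coincide.
- With a common hazard ratio of 0.3 and uptake 70% and 95%, the three hazard ratios agree at about 0.30, but the risk differences do not. Stratum differences are 3.47 points (0.95^0.3 − 0.95) and 6.89 points (0.90^0.3 − 0.90). Weighted as in the table, they give 5.18, 5.44 and 3.96 points.

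So full matching moves the hazard ratio by about 0.02 in illustration B. The large movement needs many vaccinated people to go unmatched.

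**The case against.** The strongest reply is that this is one parenthetical label. The same sentence says that hazard ratios will be obtained, Table 1 states a per-protocol contrast, and the eligibility text openly restricts the study population. Renaming the estimand changes neither the matching, nor the model, nor the pooled number. Uptake is high, distance matching is the fallback without a caliper, and former controls may re-enter as vaccinated, so the matched vaccinated may be close to all vaccinated and these not far from the population.

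Much of this stands, and it limits the size of the point. It does not rescue the label: the effect in nearly all vaccinated people is still an ATT, and the protocol fixes the term itself, so the matter is not one left to a separate analysis plan.

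Stronger readings are tempting, but the documents do not support them:

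- *That the gap is several points because the matched vaccinated are much older than the population.* On an assumed 20% of the population aged 65+, a share of 30% or 40% among the vaccinated exceeds the maximum of 24.1% or 21.7% that the quoted uptake allows. It would take heavy selective matching loss, which the protocol does not describe. The uptake figures are for the end of 2022 and enrolment ends on September 1, 2021, so uptake during enrolment may have been lower.
- *That controls are used once and run out.* The protocol states neither, so the matched-vaccinated row of illustration B is only a possibility.
- *That the hazard ratio is necessarily conditional on covariates.* Table 1, Assignment procedures, says that adjustment is done by matching, so the adjusted Cox model may be a marginal model in matched pairs.

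**Conclusion.** The label is wrong as written. The plan estimates a per-protocol hazard ratio in vaccinated people who find a match: the ATT if nearly all do, otherwise the effect in the matched vaccinated only. It is not a population average difference, and the population named in the objective is not the one that the estimate describes.

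The size of the gap cannot be derived from the protocol. On the hazard-ratio scale it is zero if the effect is homogeneous or uptake is unrelated to effect modifiers. On the assumed hazard ratios it is 0.5 to 1.2 points of effectiveness when all people aged 65+ are vaccinated and everyone is matched; other uptake patterns, or many unmatched people, could make it larger. A reader might infer that the estimate is therefore biased. That does not follow: it can be valid for the matched vaccinated while carrying the wrong name. The change is worth making because it alters what the study may conclude.

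**What to change.** 1. In the Statistical analysis plan, replace the ATE label with the per-protocol effect in the (matched) vaccinated. Name the same population in Table 1, Causal contrast of interest, and bring the objective into line.
2. Report, by country, the share of vaccinated people matched and the characteristics of those unmatched, and limit conclusions to the matched population.
3. Alongside the hazard ratio, give the difference and the ratio of cumulative incidence at a fixed time in the matched pairs. The 168 days of the target-trial column is one candidate, but the emulation column does not state that horizon, so it must be written in.

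The alternative is to keep the ATE and specify weighting or standardisation to a defined eligible population. With the present extract that population cannot include residents who have neither a dose nor a diagnosis.

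The first option costs a change of wording, a narrower stated scope and one extra output from the same matched data. The matching and the pooled hazard ratio stay as planned.

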Follow-up period	 Starts, for each individual, at randomization to one of the vaccination strategies (baseline) Ends at diagnosis of SARS-CoV-2 infection (i.e., outcome of interest), death, loss to follow-up, the date of receiving a booster dose, 168 days after baseline (24 weeks), or the end of the study period (March 1, 2022), whichever occurs first. 	 Sequential trial emulation: Starts, for each individual: Vaccine group: time of completing a primary vaccination schedule No (or partial) vaccine group: first eligible time (time of completing a primary vaccination schedule of the matched pair) Ends at diagnosis of SARS-CoV-2 infection, death (all causes), vaccination (for unvaccinated controls), completed primary vaccination of the matched control (for vaccinated persons), booster dose (for vaccinated persons), booster dose of the matched vaccinated persons), booster dose of the matched vaccinated person (for unvaccinated controls), or the end of the study period (i.e., the most recent date at which data is available at time of analysis). Loss to follow-up due to emigration or 'disenrollment' from the health care system not taken into account. Newly vaccinated individuals (completing a primary vaccination schedule) are eligible for inclusion in the "vaccine group" of the study, even if they had previously been selected in the "no vaccine group" (as controls).
Outcome	Laboratory-confirmed SARS-CoV-2 infection	A documented laboratory-confirmed SARS-CoV-2 infection, thus excluding self-reported test results
Causal contrast of interest	Per-protocol effect.	Observational analog of the per-protocol effect.

In the target trial (Figure 1), eligible participants are enrolled from January 1, 2021 (start of the SARS-CoV-2 vaccination campaign) until September 1, 2021 (start of the SARS-CoV-2 booster vaccination campaign). As such, the enrolment period in the target trial covers a

Funded by the European Union period of 9 months. For each eligible participant, follow-up starts at the moment of randomisation (baseline, t_0) and ends at diagnosis of SARS-CoV-2 infection (outcome of interest), death, loss to follow-up, receiving a booster dose, or 6 months after baseline. The period of data collection runs until March 1, 2022 to allow for a minimal follow-up period of 6 months for those participants with baseline (t_0) at the end of the enrollment period.

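### A single Cox hazard ratio per site, with pair follow-up cut by control vaccination, gives site-dependent values if effectiveness changes over time; add interval-specific HRs and pool those

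*Protocol*

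**What the plan says.** The Statistical analysis plan section of the protocol fixes the following:

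- **Effect measure.** The comparison uses "adjusted Cox proportional-hazards models", giving an HR with a robust variance. No cumulative incidence, risk ratio or HR by time since baseline is named.
- **Matching.** On each day of enrolment, people who have just completed the primary schedule "will be matched in a 1:1 ratio to unvaccinated (or partially vaccinated) controls".
- **Pair censoring.** One of the events that end follow-up is "completing primary vaccination of the matched control (for vaccinated persons"; the control's own follow-up ends at the same event. Controls are people who "may receive a first (or second) vaccination dose at a later date during the data extraction period".
- **Pooling.** Across up to seven countries or regions, "the HRs are pooled by using the inverse variance method".
- **Time-related analysis.** "Further, we can assess vaccine effectiveness during different time periods, with a dominant circulation of different SARS-CoV-2 variants". This is optional and runs on calendar time. No pooling is described for it.

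In Table 1 the target trial limits follow-up to "168 days after baseline (24 weeks), or the end of the study period (March 1, 2022), whichever occurs first". The emulation column has no such limit and runs to the latest data available. The listed sensitivity analyses cover imputation and matching algorithms only.

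**The concern.** When the hazard ratio is not constant, a single Cox HR is a weighted average of HR(t), and the weights depend on how many pairs are still followed at each t. Here that number is partly set by how fast the controls were vaccinated. In a fast roll-out most pairs end early and the HR mainly reflects early effectiveness. In a slow one it also takes in later effectiveness.

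Two sites with the same vaccine effect could therefore return different HRs. The meta-analysis would show this as heterogeneity, and the pooled HR would belong to no stated length of follow-up. The protocol's background section gives limited comparability across federations as the weakness of earlier single-country studies, so this would recreate the problem the study sets out to solve.

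**Working it through.** The protocol states no event rate, effect size or roll-out speed, so there is no figure of its own to reproduce. The calculation shows what the planned estimator targets under stated assumptions.

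**Inputs from the protocol:** 1:1 matching; a pair ends when its control completes vaccination; one Cox HR per site; inverse-variance pooling; the target trial's 168-day limit.

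**Assumptions, not in the protocol:** control hazard h = 0.0006 per day; HR(t) rising linearly from 0.10 at baseline to 0.60 at day 168; exponential pair censoring with median m.

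**Formulas, by day t:**
- Pairs not yet censored: G(t) = exp(−t·ln 2 / m).
- Risk sets: n0 = G·exp(−cumulative h); n1 = G·exp(−cumulative h·HR).
- Expected events: e0 = n0·h; e1 = n1·h·HR(t).
- The single HR, θ, solves Σ[e1 − (e0 + e1)·n1θ/(n1θ + n0)] = 0.
- For an interval HR, the sum runs over that interval only.

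**Results with follow-up limited to 168 days:**

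| Median time to pair censoring | 20 d | 40 d | 80 d | 160 d | none |
|---|---|---|---|---|---|
| Single HR | 0.184 | 0.242 | 0.290 | 0.318 | 0.348 |
| HR, first 56 days | 0.158 | 0.170 | 0.176 | 0.180 | 0.183 |
| HR, second 56 days | 0.324 | 0.337 | 0.343 | 0.346 | 0.350 |
| HR, third 56 days | 0.491 | 0.503 | 0.510 | 0.513 | 0.516 |

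The single HR implies effectiveness from 1 − 0.184 = 82% down to 1 − 0.348 = 65%, although the effect curve is the same in every column. The interval HRs move by 0.026 at most. With milder waning (0.15 to 0.50) the single HR runs from 0.209 to 0.324. With a constant HR of 0.10 it is 0.100 at every censoring speed.

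**Effect on pooling.** This is a second set of assumptions: h = 0.0002 per day; effectiveness falling log-linearly in HR from 90% to 50% by day 168; two sites of 1,000,000 pairs; medians of 14 and 120 days; var(log HR) = 1/e0 + 1/e1.

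- Fast site: HR 0.123, with 4,123 control and 510 vaccinated events. Variance = 1/4,123 + 1/510 = 0.00220; weight 454.
- Slow site: HR 0.217, with 21,267 and 4,679 events. Variance = 1/21,267 + 1/4,679 = 0.000261; weight about 3,835.
- Share of the fast site: 454/(454 + 3,835) = 10.6%. Pooled HR 0.205; Q = 131 on 1 df; I² = (131 − 1)/131 = 99%, with identical true curves.
- Pooled by 56-day interval instead, Q is 2.9, 0.4 and 0.04. In the third interval the fast site contributes about 15 control and 5 vaccinated events.

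**A 168-day risk ratio as the alternative.** Under the first set of assumptions it is 0.362 at every censoring speed, but only because the baseline hazard was flat and common to all sites. With the same total hazard and a five-fold higher hazard in the first or the last 56 days, it is 0.264 or 0.458. With two-fold waves it is 0.319 or 0.404. The share of pairs uncensored at day 168 is 0.5^(168/20) = 0.3% at a median of 20 days and 0.5^(168/40) = 5.4% at 40 days.

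**The case against.** Several objections limit the point.

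- **Waning is not in the protocol.** A reader might infer from the variant-period sentence that the plan expects non-proportional hazards. It does not say so: the sentence is optional and concerns calendar time, not time since baseline. Waning is therefore an assumption here, and without a change over follow-up nothing is distorted. This stands.
- **Roll-out speed is not given.** The protocol reports only coverage by the end of 2022 for two sites (83% in Belgium, 92% in Aragon). The medians are assumed, and 'none' fits poorly with that coverage. Between 40 and 80 days the HR moves only from 0.242 to 0.290. Nor do the documents show that control vaccination causes most of the censoring. This stands.
- **Longer follow-up.** Because the emulation has no 168-day limit, a reader might infer a far larger distortion; the same model run to 730 days gives up to 0.535. That run ignores the rule ending pairs at the vaccinated member's booster. Cutting follow-up at an illustrative 240 days lowers 0.535 to about 0.42. The difference in follow-up limit between the two columns of Table 1 is also a separate matter.
- **Replacing the HR.** A reader might infer that a 168-day risk ratio should become the main measure. It removes dependence on censoring speed only if censoring is uninformative. It still depends on each site's epidemic timing, and it rests on few pairs where the problem is greatest. Moreover, the study population excludes people with neither a dose nor a positive test, so a control who never receives a dose is in the data only because of a positive test. That distorts late control risk, and it affects the HR too.
- **Detail for a separate analysis plan.** A proportional-hazards check or extra displays could properly be left there. But the protocol itself fixes the single HR and its pooling, and that is what this point addresses.

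**Conclusion.** The point holds in a conditional form. As written, the plan can pool quantities that are not alike. If effectiveness changes with time since baseline, each site's HR depends on the speed of control vaccination and on the length of follow-up. Under the assumed waning and a 168-day limit, the single HR runs from about 0.18 to 0.35 for the same effect curve. This is an illustration, not an estimate for any of the sites. With constant effectiveness the distortion is nil.

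The optional variant-period analysis does not settle it, since it is not by time since baseline. A random-effects version of inverse variance would register the spread but would not make the HRs the same quantity. The documents support adding a measure and pooling like with like. They do not support saying that the single HR is necessarily biased, or that it must be replaced.

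**What to change.** In the common analytical pipeline:

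1. Keep the single Cox HR, and state that it and its pooled value are averages over the follow-up observed at the sites.
2. Also estimate HRs for fixed intervals since baseline within the target trial's own 168 days, for example days 0–56, 57–112 and 113–168. Pool each interval's log HR separately across sites.
3. As a supporting measure, report matched-pair cumulative incidence by arm and 1 minus the risk ratio at a common horizon, with the number of pairs still at risk. State that it depends on each site's epidemic timing.
4. Reconcile the control-censoring event, because it sets the censoring speed: Table 1 says vaccination, whereas the text says completed primary vaccination.

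The cost is some code in the shared pipeline and a few more aggregate numbers per site; no new data are needed. The drawback is wide intervals late in follow-up, above all at sites where controls were vaccinated quickly. Intervals do not remove the dependence entirely: in the first 56 days the HR still ran from 0.158 to 0.183.
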